## **6. HANDLING OF PROTOCOL VIOLATIONS: not applicable**

As this study is observational, there is no protocol violations.

## **7. HANDLING OF MISSING VALUES:**

Missing data will remain missing in all endpoint derivations except for I-QOL and PISQ-12 questionnaires for whom specific guidelines will be applied. All summary tables will be based on data without imputation of missing values.

For multivariate logistic regression (study of factors associated to success of treatment), if missing values concern most of the covariates, multiple imputation may be needed. In that case, Proc Mi & Proc Mianalyse (SAS 9.4) will be used.

Multiple imputation inference involves three distinct phases:

1. The missing data are filled in  $m$  times to generate  $m$  complete data sets. (Proc Mi)
2. The  $m$  complete data sets are analyzed using standard statistical analyses. (Proc Mi)
3. The results from the  $m$  complete data sets are combined to produce inferential results (Proc Mianalyse).

## **8. CHARACTERISTICS OF STATISTICAL ANALYSES:**

Descriptive statistics for continuous variables will be presented with  $N$ , *Mean*, *SD (standard deviation)*, *Median*, *Q1-Q3 (first and third quartile)*, where  $N$  denotes the number of subjects contributing with non-missing data.

For discrete variables, descriptive statistics will be presented with  $N$  and *percentage* of the number of subjects contributing with non-missing data in the various categories of the variable; the number of missing data will be presented but will not be taken into account in the percentage.

All statistical tests will be carried out as two-sided on a 5% level of significance. All confidence intervals will be 95% intervals.

Comparison between pre and post-operative endpoints for paired proportions will be done by a McNemar's test for binary variables.

Comparison between pre and post-operative endpoints for continuous variables will be done by a paired t-test if they are normally distributed. In case of absence of normality, the alternative is to use Wilcoxon's signed-rank test.

For both continuous or binary variables, the null hypothesis is "no difference between pre and post implantation" against the general alternative of "difference between pre and post implantation".

### For effectiveness analyses:

In order to present a smoothing scatter plot of these parameters' evolution over time, a non-parametric technique called LOESS will be used: LOESS is a type of local polynomial regression and is a generalization of moving average and polynomial regression; LOESS fits a localized regression function to data with a chosen neighborhood of points. At each point of the dataset, a low degree polynomial (linear or quadratic) is fitted to a subset of the data, with explanatory variables values near the point, whose response is being estimated: the polynomial is fitted using weighted least squares, giving more weight to points near the point whose response is being estimated and less weight to points further away. The value of the regression function is then obtained by evaluating the local polynomial using the

[figure not shown]
explanatory variables value which are in the local neighbourhood for that data point. The LOESS fit is complete after regression function values have been computed for each of the data points.

Furthermore, these repeated data are inherently unbalanced because patients did not come to all planned visits (missing data) and because the time between 2 consecutive visits is not always the same.

Consequently, specific longitudinal models must be used to take into account these unbalanced data. Mixed models containing fixed effects and random effects (intercept and/or slope) must be used and specific covariance structure to model within subject variation (R matrix) must be chosen.

If the smoothing scatter plot suggests trends with slope discontinuation over time, a mixed piecewise linear model including knots will be used.

The following pattern illustrates such piecewise linear models.

#### For safety analysis:

Incidence rates will be calculated by using:  $IR = \text{number events} / \text{number of person-years}$ .

Confidence interval will be calculated with an exact method based on the Poisson distribution. Complication free survival will be estimated by using the Kaplan-Meier method. If event date is lacking, we will impute by the middle date between visit concerned and the previous one. The distribution of mean of cumulated events over time, taking into account that multiple events per patient may occur, will also be presented, globally and stratified by the main 'high level terms'.

Standardized incidence rate may also be calculated (if data are available) in order to compare the number of side effects observed really in the Altis SU17 study, to the number expected if incidence rates stratified in year-classes and presence or no of prolapse, were the same as in general population. A SIR of 100 indicates that the number observed is equal to number expected, a SIR lower than 100 indicates than the number observed is lower than the number expected, a SIR greater than 100 indicates than the number observed is higher than the number expected. Testing if SIR is equal to 100 will be done.

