### 9.3 Safety endpoints:

A review by a Safety Committee will take place in order to classify the events declared into side effects events, technical observations and post-operative observations. This committee will also adjudicate on the relatedness of events (procedure or device), their seriousness, preferred term and classify them according the Clavien-Dindo classification).

The Safety Data Committee will adjudicate on the events reported by patients in the patient's questionnaires and not confirmed as related by the investigator.

The Clavien-Dindo is widely used throughout surgery for grading events (complications) which occur as a result of surgical procedures, grading complications by the extent of therapy necessary to resolve them.

[figure not shown]
The adjudication by the Safety Committee will be considered as the final decision.

[figure not shown]
Tables will present the following data concerning side effects occurred since implantation: type, severity, intensity, relatedness (device/procedure), Clavien-Dindo classification, Side-Effect

[figure not shown]
(=Preferred Terms when possible), SOC and High Level Term according to MedDRA, sling revisions (and description), treatments given and localization (if pain), according to time of clinically diagnosed (intraoperative vs postoperative and IUGA Time division from T1 to T4).

Incidence rates with 95% confidence interval will be calculated between operative procedure and the last follow-up visit available with an exact method based on the Poisson distribution on 'SOC' and 'High Level' terms (MedDRA classification), except for 'High Level'= pain which will be divided into 2 possible Side-Effects: 'Non urogenital pain' or 'Urogenital pain'.

The distribution of mean of cumulated events over time, taking into account that multiple events per patient may occur, will also be presented globally or stratified by the main 'High Level Term' ('Bladder storage symptoms', 'exposure and extrusion', 'Urinary Tract Infection', 'Voiding symptoms', 'pain' itself divided into 'Non urogenital pain' or 'Urogenital pain').

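### The optional standardised incidence ratio tests side effects in women operated on for incontinence against general-population rates, so a ratio of 100 is not a meaningful safety null and the bias can run either way

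*SAP*

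**What the plan says.** The SIR appears once, in SAP section 8 under safety analysis, and is conditional: "Standardized incidence rate may also be calculated (if data are available". Its purpose is "to compare the number of side effects observed really in the Altis SU17 study" with an expected number. That number comes from rates stratified by year-class and by "presence or no of prolapse, were the same as in general population". The paragraph explains ratios below, at and above 100 and ends: "Testing if SIR is equal to 100 will be done". Section 8 also fixes the level: "All statistical tests will be carried out as two-sided on a 5% level of significance". No reference source, reference rate or list of event terms is given.

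Three other places bear on it:

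- **Population.** SAP section 5 runs all analyses on women who had a procedure, including the few in whom the Altis sling was not implanted. The inclusion criteria in section 2.4 require implantation to manage urinary incontinence.
- **Event handling.** SAP 3.4 requires medical confirmation before a patient-declared complication is considered. SAP 9.3 has a committee "classify the events declared into side effects events, technical observations and post-operative observations", and adds: "This committee will also adjudicate on the relatedness of events (procedure or device").
- **Event terms.** SAP 9.3 names the main High Level Terms: "Bladder storage symptoms', 'exposure and extrusion', 'Urinary Tract Infection', 'Voiding symptoms', 'pain' itself divided" into two kinds. The list includes a category that presupposes a mesh implant.

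Section 9.3 does not mention the SIR. It plans incidence rates with exact Poisson intervals and mean cumulative events; section 8 adds Kaplan-Meier complication-free survival.

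**The concern.** An SIR is informative when the reference population differs from the cohort only in the exposure of interest, after standardisation, and when events are counted in the same way on both sides. Neither condition is met here.

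The cohort differs from the general population in having incontinence, in having had pelvic surgery and, for nearly all, in carrying a mesh. Standardising for year-class and prolapse removes none of these differences. The cohort's events pass through confirmation and classification, and the population's do not.

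If the test is run as written, a significant result in either direction could be reported as a finding about the sling when it is not one. Fewer complications than in the general population would be a striking claim for an implant. An apparent excess could equally reflect the women's underlying condition or the operation. Monitoring safety is part of the protocol's main objective, so a reader would give such a result weight.

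**Working it through.** The SAP states no SIR, expected count, reference rate or power for this test, so there is no figure to reproduce. The calculations below only show how the ratio behaves.

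**Inputs**

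- Cohort: about 600 women (SAP 2.2).
- Follow-up: procedure to last available visit, up to 3 years, so at most 600 × 3 = 1,800 person-years. Assumed: 1,500 (600 × 2.5), range 1,200 to 1,800.
- General-population rate for non-mesh events: not given. Assumed: 0.05 per person-year, range 0.02 to 0.10.
- Test: two-sided 5% (SAP section 8), taken as exact Poisson.

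**Formulae.** Expected E = rate × person-years = 0.05 × 1,500 = 75. SIR = 100 × O/E. Limits are exact Poisson (chi-square).

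**1. Filtered numerator, real excess.** Suppose the true all-cause rate is 50% above background (true SIR 150), all caused events are counted, and a share c of background events survives the committee's sort. Then O = E × (c + 0.5), rounded.

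| c | O | SIR (95% CI) | p |
|---|---|---|---|
| 1 | 112 | 149 (123 to 180) | <0.001 |
| 0.5 | 75 | 100 (79 to 125) | 1 |
| 0.25 | 56 | 75 (56 to 97) | 0.027 |
| 0 | 38 | 51 (36 to 70) | <0.001 |

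The point estimates barely move over the assumed ranges, but significance does. For c = 0.25:

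- rate 0.02, 1,500 person-years: 22/30, SIR 73 (46 to 111), p = 0.16;
- rate 0.05, 1,200 person-years: 45/60, SIR 75 (55 to 100), p = 0.053;
- rate 0.10, 1,500 person-years: 112/150, SIR 75 (61 to 90), p = 0.001.

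**2. All events counted, no device effect.** Suppose background in these women is k times the general-population rate. Then O = 75k, rounded.

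| k | O | SIR (95% CI) |
|---|---|---|
| 1.25 | 94 | 125 (101 to 153) |
| 1.5 | 112 | 149 (123 to 180) |
| 2 | 150 | 200 (169 to 235) |

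All three are significantly above 100 although the device does nothing.

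**3. Mesh exposure and extrusion alone.** Assume 10 observed events in 1,500 person-years. Reference rates of 0.001, 0.0001 and 0.00001 give E = 1.5, 0.15 and 0.015, and SIR = 667, 6,667 and 66,667. With a reference rate of exactly zero the ratio is undefined. The value is set by the reference rate and says nothing about the sling.

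**4. Pooled over terms.** Adding those 10 mesh events, with no expected count, to the last row of step 1 gives (38 + 10)/75 = 64 (47 to 85). This can be computed, but the mismatch remains.

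**The case against.** The strongest reply is that little rests on this analysis. It is worded as a possibility, depends on data being available and is absent from section 9, where the planned analyses are set out. The availability condition may itself exclude terms with no reference rate, which is the mesh case. The protocol and SAP ask that device-related events be documented, and the other safety analyses do that without the SIR. All of this stands, and it is why the point is minor. It does not repair the comparison if the SIR is run: the comparator and the null are stated.

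Two stronger readings are tempting, and the documents do not support them.

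- **That the SIR would make the device look falsely safe.** A reader might infer that unrelated events are removed from the observed side only. The SAP does not say so. The paragraph speaks of side effects, not related side effects. The sort in 9.3 is into side effects, technical observations and post-operative observations, and 9.3 then tabulates relatedness as a descriptor of side effects. A related-only numerator is a possible reading, since relatedness is adjudicated, but it is not stated. If all events count, step 2 shows that the bias can go the other way.
- **That the SIR is undefined for mesh events.** This holds only for a separate SIR on that term with a reference rate of exactly zero. The SAP does not say the SIR is calculated by term, and nothing says that the general population excludes women with mesh.

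The numbers can also be called circular, because rates, person-time and retained shares are all assumed. That is fair: they show what could happen and do not measure a defect.

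**Conclusion.** The comparison is unsuitable as written, and its bias has unknown direction. SIR = 100 against the general population is not a meaningful safety null for women operated on for incontinence, because the reference ignores incontinence, surgery and mesh, and because events are confirmed and classified on one side only. This conclusion follows from the SAP's wording and needs no assumed rate.

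The possible size does rest on assumptions. With 75 expected events, a true 50% excess can appear as SIR 51 to 75 when a quarter or fewer of background events are counted. A device with no effect can appear as SIR 125 to 200 when background is 1.25 to 2 times the population's. The documents do not say which case applies.

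Severity is minor: the analysis is optional, and no primary endpoint, sample size or success definition uses it.

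**What to change.** Delete the test of SIR = 100 against the general population. Rely on the incidence rates with exact Poisson intervals, the Kaplan-Meier complication-free survival and the mean cumulative events, all already in the SAP.

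If the sponsor wants an external comparison, the SAP should:

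- name a reference cohort of women having sling surgery for incontinence, and its source;
- apply the same event definitions and the same relatedness rule to both sides, and state that rule;
- limit the comparison to terms that have a reference rate in that cohort;
- report it descriptively, without a test.

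The documents identify no such cohort, so whether a suitable one exists is for the sponsor to establish. The cost is a change of SAP wording and the loss of one optional table; no data collection changes.

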#### **A. Factors associated with treatment success:**

Factors associated with treatment success will be assessed through logistic regression:

Univariate models will be performed with all variables suspected or known to be linked with treatment success such as age, BMI, SUI vs MUI, Pelvic Organ Prolapse, cause of stress component, active lifestyle, smoker, diabetes mellitus, recurrent UTI, severity of urinary incontinence (number of pads /day), Chronic bronchitis/cough (COPD), surgical incontinence treatment (bulking agents, sling, burch...), previous conservative treatments (pelvic floor exercise, biofeedback, bladder training, electrical vaginal stimulation), previous treatment by medication (oestrogen), post menopause, neurological disorders, PVR > 100 ml, preexisting dyspareunia, hysterectomy, relevant non obstetrical/gynecological surgery or medical history and other relevant disease.

- 1) For continuous variables, different cut-off will be used and the optimal threshold will be chosen by comparing AIC.
- 2) Only variables associated with  $p < 0.20$  in the univariate models will be selected for the multivariate models. Backward, forward or stepwise effect selection methods will be used.

**B. Factors associated with complications:** voiding symptoms and non-urogenital pain:

Factors associated with first occurrence of voiding symptoms or non-urogenital pain will be assessed through survival analysis (Cox model):

- 1) Univariate models will be performed with all variables suspected or known to be linked with voiding symptoms or non-urogenital pain such as:
  - For voiding symptoms: age, POP repair (medical history), POP repair (concomitant surgery), neurological disease/condition, abnormal bladder capacity (>500 ml), abnormal PVR (>50mL), abnormal PVR (>100mL), concomitant medication, obesity, menopause, Pelvic floor muscles training/exercises...
  - For non-urogenital pain: age, lifestyle, hysterectomy, POP repair (medical history), concomitant pelvic surgery, Altis surgery duration ...

For continuous variables, different cut-off will be used and the optimal threshold will be chosen by comparing AIC.

- 2) Only variables associated with  $p < 0.20$  in the univariate models will be selected for the multivariate models. Backward, forward or stepwise effect selection methods will be used.

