## 2.2 Sample size:

Effectiveness of female SUIs managed with sling implantation is not accurately defined and large range of success of the procedure is reported.

Furthermore, definition of success is not standardized and comparison across studies and systems is not feasible due to different used endpoint criteria.

Accordingly if  $p$  is the % of success as defined in this protocol, the product  $p*(1-p)$  should be maximized. According to the interim results of an US study, the PGI score at 1 year is 89.3 %.

So this hypothesis of a 89 % rate could be chosen. Therefore, the minimal sample size to be included to detect this prevalence with a 5 % precision is given as following:

$$n = z^2 p(1-p) / d^2.$$

Precision ( $d$ ) = 5 %      prevalence ( $p$ ) = 89 %      estimated sample size  $n = 150$

The total number of subjects enrolled is not limited. However, a minimum of 150 subjects with 12-month available data will be collected. Taking into account a global attrition rate of 20%, 180 patients are targeted for enrolment.

When 150 subjects will have reached a minimal 12-month follow-up duration and all cases are judged exploitable, Sponsor will take the decision to stop or to continue the current recruitment.

Consequently, the centers have been encouraged to keep on enrolling patients after the first 180 patients defining an open-ended recruitment. Approximately 600 patients have been finally included.

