### 3. VARIABLES TO BE SUBJECTED TO STATISTICAL ANALYSES:

#### 3.1 At baseline:

- *Subject's demographics & Medical History:*
  - Age (+ sub groups: <65 and  $\geq 65$  year-old)
  - BMI (+ sub groups: lower-normal/over/obesity) (< 25/ 25-29,99 /  $\geq 30$ )
  - Lifestyle (active, sedentary)
  - Smoking status
  - Comorbidities/medical/surgery/uro-gynecological history including Pelvic organ prolapse / hysterectomy / SUI
  - Menopausal status
  - Category of urinary incontinence (SUI, MUI, UUI, other UI)
  - Duration and cause of stress component (+ subgroups: < 5 years and  $\geq 5$  years)
  - Previous treatments of UI (including combined antimuscarinics and mirabegron)
  - Preexisting symptoms (dyspareunia / urgency symptoms)
- *Physical examination:*
  - Clinical tests :
    - Cough stress test
    - Cervico-urethral mobility (Marshall/Bonney Test, Ulmsten Test, Q Tip/cotton swab Test, other)
    - POP-Q:
      - If POP by grade and localization (anterior vaginal wall, apical, posterior vaginal wall)
      - POP associations
- *Nb of pads used/day (and by number of pads)*
- *Pad weight test (if done)*
- *Urodynamics testing (if done):*
  - maximum urine flow rate (+  $Q_{max} < 15$  ml)
  - post-void residual volume measurement (+ PVR > 150 ml)
  - Cystometry:
    - normal
    - bladder outlet obstruction,
    - detrusor over or underactivity,
    - urodynamic SUI
  - Measures of urethral pressure: (one of following methods)
    - MUCP
    - VLPP

- ALPP

- *Questionnaire ICIQ –UI-SF*

- Sum items 3+4+5
- Items 6

○ *Questionnaire I-QOL:*

- total scores and subscale scores: Avoidance and Limiting Behavior (ALB), Psychosocial Impacts (PS), and Social Embarrassment (SE).
- demographic questionnaire

○ *Questionnaire PISQ 12:*

- total scores
- Q5, Q6 and Q7 separately

3.2 Operative procedure:

- *Surgical Procedure :*

- Type of anesthesia
- Pre and intra-operative antibiotics
- Concomitant pelvic surgery (type): hysterectomy and/or surgical cure of a pelvic organ prolapse, association, other
- Blood loss
- Intra-op complications
- Duration
- Technical observations

- *Immediate post-operative data:*

- Post –operative antibiotics and duration
- Spontaneous post-op micturition or urinary drainage and duration
- Postoperative hospital stay/duration
- Post-void residual volume at discharge
- Maximum flow rate at discharge (if done)

3.3 follow up visits from first postoperative visit until 3 years after implantation:

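### Choosing each continuous factor's cut-off by best AIC and then testing it at the nominal 5% level inflates false prognostic factors in SAP section 8, parts A and B

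*SAP*

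**What the plan says.** SAP section 8, part A, plans logistic regression for factors associated with treatment success. It names 21 candidates in a list left open at both ends. On continuous candidates it says: "For continuous variables, different cut-off will be used and the optimal threshold will be chosen by comparing AIC". Variables with univariate p<0.20 go forward, and then: "Backward, forward or stepwise effect selection methods will be used". It does not say which of the three methods applies, at what entry or stay level, or how many cut-offs are tried over what range.

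Part B repeats these rules for Cox models of first voiding symptoms and first non-urogenital pain.

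The general rule in section 8 is: "All statistical tests will be carried out as two-sided on a 5% level of significance". Neither part provides a correction for the cut-off search, a multiplicity adjustment, shrinkage or internal validation.

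SAP section 3.1 already lists groupings for some of the same variables: age below 65 against 65 and over, and "BMI (+ sub groups: lower-normal/over/obesity" with limits at 25 and 30. Nothing ties these groups to the regressions.

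The protocol synopsis and SAP section 1 both describe the prognostic aim as exploring.

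**The concern.** A p-value has its nominal meaning only if the comparison was fixed without looking at the outcome. Here the outcome picks the split, and the split is then tested on the same data. A factor with no effect gets several chances to look significant and keeps its best one. The estimate at that split is biased away from the null for the same reason.

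Pre-surgery prognostic factors are a stated secondary objective. A threshold for age, BMI or pads per day that is reported as optimal also invites use as a patient-selection rule, which makes a spurious one costlier than an ordinary false positive in a table.

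**Working it through.** **1. The plan's own figure.** SAP section 2.2 takes its success rate from another study: "According to the interim results of an US study, the PGI score at 1 year is 89.3" per cent; it then says "So this hypothesis of a 89 % rate could be chosen". With z = 1.96, p = 0.89 and d = 0.05:

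n = 1.96² × 0.89 × 0.11 / 0.05² = 150.4.

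This reproduces the stated 150. That calculation concerns the precision of one proportion. The SAP gives no failure count and no error rate for the prognostic models.

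**2. Number of failures in part A (an assumption).** Section 2.2 gives about 600 patients included and 20% attrition. Then 600 × 0.80 × 0.11 = 52.8, or about 53.

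- Low end: 480 women at 95% success, 480 × 0.05 = 24.
- High end: 600 women at 75% success, 600 × 0.25 = 150.
- Failures per named candidate: 53/21 = 2.5, with a range from 24/21 = 1.1 to 150/21 = 7.1.

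**3. Why best AIC means smallest p-value.** AIC = 2k − 2 log L. Every single-threshold split of a variable has the same k, so the lowest AIC is the highest likelihood. That is also the largest likelihood-ratio statistic and hence the smallest p-value.

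**4. One searched variable with no effect.** Simulation with 480 women and 11% failures, 4,000 data sets per setting, likelihood-ratio test at the best cut-off. Ranges cover repeat runs.

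| Cut-offs tried | Nominal p<0.05 | Passes p<0.20 screen |
|---|---|---|
| 1 (fixed) | 5% | 20% |
| 3 | 13-14% | 42-44% |
| 9 | 25-26% | 70% |
| 17 | 31-32% | 77% |

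With 66 failures of 600, or 20% failures, the p<0.05 rates hardly move. With 5% failures they are 13%, 31% and 37% for 3, 9 and 17 cut-offs. The median odds ratio of a falsely significant factor was about 2.1 to 2.3, although the true value is 1.

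**5. Which variables are searched.** In part A the named continuous candidates are age, BMI and pads per day, so 3 of 21. Post-void residual (PVR) is already entered as above 100 ml. In part B they are age (both outcomes) and surgery duration (pain only); bladder capacity, PVR and obesity are already categorised.

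**6. The whole part A procedure with no true factor.** Without any search, 21 independent tests at 5% give 1 − 0.95²¹ = 0.66 for at least one false positive, and 21 × 0.20 = 4.2 variables pass the screen on average. The full sequence was simulated with 3 continuous and 18 binary independent candidates, the p<0.20 screen, then backward elimination at 0.05 (1,500 runs per cell). The 0.05 stay level and the number of cut-offs are assumptions, because the SAP leaves both open.

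| Women / failures | No search (linear) | 4 cut-offs | 17 cut-offs |
|---|---|---|---|
| 480 / 53, at least one false factor | 62% | 74% | 83% |
| 600 / 66, at least one false factor | 63% | 75% | 83% |
| 480 / 96, at least one false factor | 67% | 75% | 85% |
| 480 / 53, mean number of false factors | 0.99 | 1.37 | 1.70 |

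In the 480/53 setting a continuous variable reaches univariate p<0.05 in 5%, 15% and 27% of runs respectively. The 27% is below the 31-32% in step 4 because this run used Wald tests, which are more conservative when failures are few. The search adds 73.6 − 62.4 = 11 to 83.2 − 62.4 = 21 percentage points to the chance of any false factor. The rest comes from screening and selecting among many candidates. The full sequence was not run at 24 or 150 failures.

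**The case against.** The strongest defence is that the analysis is secondary, is called exploratory in both documents, and leaves the primary success rate untouched. That stands, and it limits the consequence. It does not make the p-values valid, because the SAP applies its two-sided 5% level to all tests and gives no caveat for these models.

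It is also fair that the search reaches few variables, and that most of the any-false-factor rate exists without it (62% against 74-83%). The several-fold inflation holds per searched variable, not for the procedure as a whole.

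A reader might infer more than the documents support:

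- **That there are about 53 failures.** The documents do not say so. The 89% rests on a PGI-only result from another study, and the 20% attrition was planned for a target of 180. The composite endpoint adds adverse-event failures, and the Scientific Committee definition also drops the little-better answer. Part A does not say which definition is modelled.
- **That the same numbers apply to part B.** No event counts are given there, the candidate lists are shorter, and hazard ratios were not simulated. The criticism of the rule carries over; the figures do not.
- **That reported factors would mostly fail to replicate.** The simulations assume no candidate has any effect, whereas the SAP chooses candidates suspected or known to matter. No scenario with true effects was run.
- **That the rule overrides the section 3.1 groups, including duration of the stress component.** Those groups are not prescribed for the regressions, and part A names the cause of the stress component, not its duration. The two sections are unreconciled, which is less than a contradiction.
- **That one sparse covariate would empty the model.** Section 7 does say "if missing values concern most of the covariates, multiple imputation may be needed", a high bar. But no missingness rate is available, and a covariate reduces the multivariable set only if it passes the screen.

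**Conclusion.** The concern holds for the cut-off rule. Followed as written, it yields p-values that do not keep the stated 5% level: about 13-14% to 31-32% per searched null variable for 3 to 17 cut-offs. It also exaggerates the odds ratios at the chosen cut-offs. The exact inflation is not determined by the plan, because the number of cut-offs is open.

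Screening and unspecified automatic selection compound this in part A. At least one false factor appears in about 74-83% of runs when nothing is truly associated. This rests on independent candidates, 4 or 17 cut-offs, a 0.05 stay level and an assumed 53 failures, and it changes little up to 96 failures of 480.

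For part B the flaw is the same in kind, but its size is unknown. The effect is confined to an exploratory secondary objective and does not reach the primary estimate.

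**What to change.** **Main change.** Delete the AIC cut-off search from parts A and B. Enter age, BMI, pads per day and surgery duration as continuous terms, linear or restricted cubic spline. Alternatively, use only cut-offs fixed before the data are seen, such as the section 3.1 age and BMI groups. Section 3.1 cannot supply every cut-off: it gives no grouped limit for pads. Its PVR limit is above 150 ml, while part A uses above 100 ml and part B lists above 50 ml and above 100 ml. These PVR thresholds must be reconciled.

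This alone returns the per-variable error rate to about 5%, but the chance of some false factor stays near 62%.

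**Preferably also.** Close the candidate list and fit the pre-listed factors in one model without the univariate screen. If selection is kept, fix one method and its stay level, report bootstrap optimism-corrected estimates, and label the p-values as not controlling the 5% level. Penalised regression is an option, not a requirement.

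**Cost.** SAP wording and moderate programming, with no new data. The downside is fewer significant factors and no single cut-off to quote.
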